8.1 Requirements for Investigators to Enter Data

Investigators must ensure that all data is entered into the case report form truthfully, accurately, completely, timely, and in compliance with applicable laws and regulations.

- 8.1.1 For all patients who have signed the informed consent form and been screened eligible for the trial, investigators must carefully and thoroughly record all observed information in the case report form, ensuring no items are left blank or omitted.
- 8.1.2 All data in the case report form must be verified against the original medical records of the subject to ensure accuracy.
- 8.1.3 The case report form serves as the original data. Any corrections must be made by striking through the original text, adding notes in the margin, and signing and dating the correction by the researcher.
- 8.1.4 Original laboratory test results (or copies of original laboratory test results) must be affixed to the designated section for laboratory test results in the study medical records.
- 8.1.5 Data that is significantly higher or lower than expected or outside the clinically acceptable range must be verified or rechecked, and the researcher must provide necessary explanations.

8.2 Database Establishment and Data Entry/Storage

- 8.2.1 Database Establishment: Data programmers will construct the database interface based on CRF or eCRF documentation and perform logical validation programming in accordance with the DVP.
- 8.2.2 Data Entry: CRCs or investigators will be responsible for data entry according to the eCRF completion guidelines.
- 8.2.3 Data Review: CRAs will perform SDV on the data and send any inconsistent data to the clinical team for resolution.
- 8.2.4 The EDC system has both system-generated and manual query modes. When abnormal data is entered, the EDC system will issue real-time alerts to prompt the data entry personnel to verify the data. Data managers will conduct manual reviews of the data and raise queries for any issues identified.
- 8.2.5 The clinical research implementation unit shall ensure the traceability of clinical data and retain all original data in its entirety. All original documents, data processing records, and related materials shall be retained by the participating hospitals for a period of 10 years following the completion of the clinical study.

8.3 Specimen Collection, Storage Facilities, and Laboratory Premises

The specimen collection, storage facilities, and laboratory premises for this trial are located at each center.

9 Requirements for Reporting Adverse Events

9.1 Definition of Adverse Events

(1) Adverse Event (AE): An unfavorable medical event occurring during the clinical trial, regardless of whether it is related to the trial.

(2) Serious Adverse Event (SAE): An adverse event that results in death or a serious deterioration in health, including fatal diseases or injuries, permanent defects in bodily structure or function, hospitalization or prolongation of hospitalization, medical or surgical intervention to prevent permanent defects in bodily structure or function; fetal distress, fetal death, or congenital anomalies, or congenital defects.

Note: The following situations do not constitute SAEs:

- a) Hospitalization that was already planned prior to screening and did not result in a serious deterioration in health;
- b) Expected, non-worsening fluctuations in pre-existing or detected abnormal conditions or diseases at the time of screening;
- c) Hospitalization or prolonged hospitalization during the clinical study period as specified in the protocol (if applicable).

9.2 Reporting Procedures

- (1) In the event of any adverse event, investigators shall promptly report and file a report with the principal investigator, the clinical trial institution, the ethics committee, and the sponsor.
- (2) In the event of a serious adverse event during a clinical trial, investigators shall immediately take appropriate therapeutic measures for the subject, simultaneously submit a written report to the medical device clinical trial management department of the clinical trial institution to which they belong, and notify the sponsor in writing through such department. The medical device clinical trial management department shall report the incident in writing to the relevant ethics committee and the food and drug supervision department and health and family planning authority of the province, autonomous region, or municipality where the clinical trial institution is located within 24 hours. In the event of a death, the clinical trial institution and the investigator shall provide the ethics committee and the sponsor with all necessary information.
- (3) For serious adverse events and device defects that may lead to serious adverse events, the sponsor shall report to the food and drug supervision and administration department and the health and family planning authority at the same level within 5 working days of becoming aware of the event, and shall notify other clinical trial institutions and investigators participating in the trial, and the medical device clinical trial management department shall promptly notify the ethics committee of the clinical trial institution.

Reference

- national cross sectional study. BMJ. 2020 Apr 28;369:m997.
- 3. Bohannon NJ: Individualized treatment of type 2 diabetes mellitus using noninsulin agents: clinical considerations for the primary care physician. *Postgrad Med* 2012, 124(4):95-108.
- 4. American Diabetes Association: 6. Glycemic Targets: Standards of Medical Care in Diabetes-2018. *Diabetes Care* 2018, 41(Suppl 1):S55-S64.

This Statistical Analysis Plan (SAP) has been prepared for the clinical trial titled:

“A Multicenter, Randomized Controlled Clinical Trial to Evaluate the Interventional Value of Glycated Albumin (GA) in Glycemic Control for Patients with Type 2 Diabetes Mellitus”

sponsored by Asahi Kasei Pharma Corporation. This document provides a detailed description of the statistical analysis methods and procedures to be applied in the study.

The SAP is based on the Protocol Version 3.0 dated March 8, 2023, and the Case Report Form (CRF) Version 3.0 dated February 1, 2024.

2. Research Objective

The objective of this study is to verify the hypothesis that:

“Adjusting treatment regimens based on GA test results is more effective in helping patients achieve target average blood glucose levels (HbA1c).”

3. Research Design

3.1. Research groups

Subjects will be randomly assigned to two groups:

- Intervention Group (Group A)
- Control Group (Group B)

Each group will consist of 100 subjects. Randomization will be performed using block randomization generated by SAS version 9.4 or later, ensuring reproducibility. Randomization letters will be used to assign eligible subjects in a 1:1 ratio to either Group A or Group B.

All subjects will receive antidiabetic treatment according to standard clinical practice. The use of sulfonylureas, glinides, insulin, or insulin analogs is prohibited in this study.

At the first follow-up visit (Month 1), GA will be measured for subjects in the intervention group. Based on the GA normalization principle, the investigator will adjust the treatment regimen accordingly. At Month 2 and Month 3, blood samples will be collected, and GA will be measured after the follow-up period,

but these results will not be used to adjust treatment and will be used only for statistical analysis.

Subjects in the control group will also have blood samples collected at Month 1, Month 2, and Month 3, with GA measured after the follow-up period for statistical analysis only.

3.2 Study Procedures and Follow-up Schedule

The research steps and follow-up plan are shown in Figure 1 and Table 1.

[figure not shown]

Figure 1. Research process diagram

Table 1 Research flowchart

	Screening visits	Baseline [#]	Follow-up				Measurement of GA Frozen sample
Visit number	1	2	3A	3B	4	5	
visit time	Days -7 to 0	Day 0	4 weeks (baseline: 28 ± 3 days)	4 weeks (follow-up visit 3A + 5 days) [*]	8 weeks (baseline 56 \pm 3 days)	12 weeks (baseline 84 \pm 3 days)	Follow-up visit completed
informed consent	X						
Demographic information (name,	X						

gender, ethnicity, date of birth)							
Medical history ^a	X						
Physical examination ^b	X		X ^h	X ^g	X	X	
Collect samples and perform the following laboratory tests:							
Blood glucose-related tests ^c	X ⁱ					X	
Complete blood count ^d	X ⁱ					X	
Liver and kidney function ^e	X ⁱ					X	
lipids ^f	X ⁱ					X	
Blood or urine pregnancy test	X ⁱ						
Blood sample collection (for GA measurement)	X		X ^h		X		
Inclusion/exclusion criteria	X	X					
Confirm eligibility for enrollment		X					
Randomization		X					
Treatment plan		X					
Distribution of subject diaries		X	X ^h	X ^g	X		
Check and collect participants' report			X ^h	X ^g	X	X	
GA measurement			X ^g			X	
Adjust treatment plan			X ^h	X ^g	X		
Recording medication treatment	X	X	X ^h	X ^g	X	X	
Record and review		X	X ^h	X ^g	X	X	

(since the previous visit)						
(S) AE						
study termination					X	
Determination of GA in frozen samples						X

Notes:

- #If screening and baseline are conducted on the same day, all duplicate steps need only be performed once
- *It is best to conduct the visit within 3 days after the 3A visit, with a maximum of 5 days
- a. Medical history includes information such as disease course and treatment methods
- b. Physical examination includes: height, weight, waist circumference, blood pressure, pulse (screening period); weight, waist circumference, blood pressure, pulse (follow-up period)
- c. Blood glucose-related tests include: fasting blood glucose, HbA1c, fasting C-peptide, fasting insulin
- d. Complete blood count: red blood cells (RBC), white blood cells (WBC), platelets (PLT), hemoglobin (HGB)
- e. Liver and kidney function: total bilirubin (Tbil), alanine transaminase (ALT), aspartate transaminase (AST), total protein (TP), albumin, blood urea nitrogen (BUN) or urea (Urea), serum creatinine (Cr), uric acid (UA)
- f. Lipid profile: Total cholesterol (TC), triglycerides (TG), low-density lipoprotein (LDL-C), high-density lipoprotein (HDL-C)
- g. Only for Group A participants
- h. Only for Group B participants
- i. If the patient has laboratory test results within the past 7 days, historical results may be used, and repeat testing is not required.

3.3. Sample size

Each group (Intervention and Control) will include 100 subjects.

The sample size was determined based on a preliminary single-center pilot study (n=40), which showed that the proportion of subjects achieving HbA1c < 7% after 3 months was 76.9% in the intervention group and 46.2% in the control group (p = 0.226).

Assuming:

- $\alpha = 0.05$ (two-sided significance level)
- Power = 0.8
- Effect size = 30% difference between groups

Considering factors such as:

- Follow-up completion rate in the pilot study (72.5%)
- Multicenter design

The target sample size was calculated to be 100 subjects per group.

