3.5 Sample size

100 cases each in the intervention group and the control group. Sample size calculation method:

In our previous single-center pilot study (n=40) targeting this research, the results showed that patients whose treatment regimens were adjusted based on GA achieved an HbA1c target rate (<7%) of 76.9% at 3-month follow-up, compared with 46.2% in the control group (p=0.226). Statistical significance was set at P < 0.05, with a statistical power of 0.8 and a 30% difference between the experimental and control groups as the calculation basis. Considering the follow-up completion rate of the pre-experimental patients (72.5%) and other factors such as a multi-center study, the target sample size for this study was determined to be 100 cases each for the intervention and control groups.

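### Does it matter that the stated inputs give about 53 to 68 per arm when the plan says 100 was calculated?

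*SAP*

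**What the plan says.** Protocol 3.5 and SAP 3.3 use the same inputs. The Protocol says "Statistical significance was set at P < 0.05, with a statistical power of 0.8"; the SAP adds that this is a "two-sided significance level" and gives "Effect size = 30% difference between groups". The difference comes from a "preliminary single-center pilot study (n=40" patients), with HbA1c <7% reached by "76.9% in the intervention group and 46.2% in the control group (p = 0.226").

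Both documents then adjust for the pilot's 72.5% follow-up completion and for the multicentre setting. The Protocol describes the latter as one of several other factors. The SAP ends with "The target sample size was calculated to be 100 subjects per group"; the Protocol says only that the target was determined. Neither gives a formula, an evaluable number before adjustment, or the size of the multicentre allowance. Neither states the power or detectable difference that 100 per arm delivers.

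**The concern.** A sample size described as calculated should be reproducible from its inputs, and this one is not. The natural suspicion is an arithmetic slip or a missing input. The multicentre explanation also looks weak, because patients are individually randomised 1:1 and Protocol section 6 plans 10 + 10 per centre, a design that ordinarily needs no inflation for clustering.

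The pilot figures raise a second doubt: the percentages and p-value point to fewer analysed patients than 72.5% of 40. If so, the retention assumption would be more optimistic than the pilot's evaluable rate.

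At stake would be how a null result is read. Someone who takes the section to mean 80% power for 30 points and no more would underestimate what the trial can detect.

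**Working it through.** **Inputs.** Two-sided α = 0.05, power 0.80, 1:1 allocation, completion 0.725 (SAP 3.3). Rates: 76.9% vs 46.2% (pilot); 76.2% vs 46.2% (exactly 30 points); 65% vs 35% (the 30-point difference with the largest variance).

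**Evaluable number per arm**, with p̄ the mean of p₁ and p₂ and d = p₁ − p₂:

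n = [1.96·√(2p̄(1−p̄)) + 0.842·√(p₁(1−p₁) + p₂(1−p₂))]² / d²

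With continuity correction: n_c = (n/4)·[1 + √(1 + 4/(n·d))]². Randomised number = n/0.725.

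| Rates | n | n/0.725 | n_c | n_c/0.725 |
|---|---|---|---|---|
| 76.9 vs 46.2 | 38.2 | 52.7 | 44.5 | 61.4 |
| 76.2 vs 46.2 | 40.2 | 55.5 | 46.7 | 64.3 |
| 65 vs 35 | 42.4 | 58.5 | 48.8 | 67.4 |

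Exact power for Fisher's test gives 44 to 49 evaluable and 61 to 68 randomised. Even 90% power with continuity correction reaches at most 87. So 100 is not reproduced; the unexplained factor runs from 100/67.4 = 1.5 to 100/52.7 = 1.9.

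**What 100 per arm delivers, completers only.** For the three rate pairs, power is 96 to 97% with 72 completers per arm (100 × 0.725 = 72.5) and 94 to 96% with 65. Power of 80% is reached at about 23 and 24 points respectively.

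**If missing Visit 5 values stay in the denominator.** SAP 4.1.1 divides by everyone in the analysis set, SAP 6 requires only a baseline measurement for the FAS, and SAP 7.2.1 rules out imputation. Read literally, patients without a Visit 5 HbA1c count as not reaching target.

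- At 72.5% observed, 76.9% and 46.2% become 0.769 × 0.725 = 55.8% and 0.462 × 0.725 = 33.5%, a difference of 22.3 points. That needs 78 per arm (86 with continuity correction), and power at 100 is 89%. Across the three rate pairs the need is 76 to 90 and power is 88 to 90%.
- At 65% observed, 76.2% and 46.2% become 49.5% and 30.0%. That needs 98 per arm (108 corrected), and power at 100 is 81%. Across the three pairs, power is 81 to 84%.

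**Pilot denominators.** 10/13 = 76.9% and 6/13 = 46.2%, with Fisher p = 0.2262. The only other arm sizes within 40 patients that fit the percentages are 13 with 26 (p = 0.093) and 26 with 13 (p = 0.077). The pilot's HbA1c <6.5% rates (Protocol sections 1 and 4), 30.8% and 23.1%, are 4/13 and 3/13. So 26 of 40 (65%) were probably analysed, against 29 of 40 = 72.5% who completed. Using 65% in place of 72.5% raises the requirement only to 60 to 76 per arm, so it does not explain 100 either.

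**The case for a change.** The strongest case for a change is that a figure called calculated should be traceable, and that the one named reason for the extra patients is not a standard ground for inflation in this design. Depending on choices the section leaves open, achieved power runs from about 81% to 97%. The pilot difference has a 95% CI of about −5 to +66 points, so the detectable difference is what a reader of a null result would want. Rewording would cost no enrolment.

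The lack of traceability stands. The rest carries less weight:

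- The multicentre allowance is a listed input without a number, so the arithmetic cannot be called wrong. It need not mean clustering. A single-centre effect may shrink across centres whose physicians choose the drugs, and a 23-point difference (69.2% vs 46.2%) needs 71.2/0.725 = 98 per arm. The documents do not say that this was the reasoning.
- The 26 analysed patients are inferred, and 29 completers with 26 usable HbA1c values is consistent.
- A null result will be read from the 95% CI for the difference, which SAP 7.4.1 already requires.
- A restatement of 94 to 97% power would hold only for a completers-only analysis and would overstate power under the SAP 4.1.1 denominator.
- The SAP rests on Protocol version 3.0, while version 2.0 is the one available; the derivation may be set out there.

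**Conclusion.** No change follows. The plan does not show how 100 per arm was reached, and its quantified inputs account for only 53 to 68. The gap is in the conservative direction, and no stated figure is shown to be false. On the plan's own inputs (30 points, 72.5% completion), 100 per arm exceeds 80% power whether the analysis uses completers (96 to 97%) or keeps missing values in the denominator (88 to 90%).

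The thinnest margin needs two things outside those inputs: 65% of patients observed, and missing counted as failure. Uncorrected power is then 81 to 84%; with a continuity correction the requirement is 100 to 108 per arm, so power could fall marginally below 80%.

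These results assume that the true rates are near the pilot's, or differ by 30 points, and that observation is equal in both arms. What is missing is background detail: the formula, the size of the allowance and the pilot denominators. Supplying it would alter neither enrolment nor any analysis.

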3.4. Expected Overall Duration of the Clinical Trial

Considering the time required for clinical trial institutions to complete patient enrollment, follow-up, and sample testing, the study is expected to take 18 months from the first patient enrollment to database lock. If the implementation time exceeds the expected duration, the protocol will not be modified.

4. Study Endpoints

4.1. Efficacy Endpoints

4.1.1. Primary Endpoints

Proportion of subjects achieving HbA1c < 7% at Visit 5 (Week 12 ± 3 days)

Percentage of subjects == (Number of subjects with HbA1c < 7%) / (Total number in efficacy analysis set) × 100%

The efficacy analysis set includes:

- Full Analysis Set (FAS)
- Per Protocol Set (PPS)

4.1.2. Secondary Endpoints

Secondary endpoints include:

- Proportion of subjects with HbA1c < 6.5% at Visit 5
- Proportion of subjects with HbA1c < 6.0% at Visit 5
- Change in HbA1c from screening to Visit 5
- Incidence and frequency of hypoglycemia
- Change in pancreatic β-cell function
- Change in insulin resistance
- Change in body weight
- Change in waist circumference
- Change in BMI

All secondary endpoints will be evaluated as changes from screening to the end of treatment (Visit 5), including absolute and percentage changes.

4.2. Safety indicators

4.2.1. Exposure time: Not applicable.

4.2.2. Adverse events (AEs)

Adverse event(AE):

Adverse medical events that occur during the clinical trial, regardless of whether they are related to this trial.

Serious Adverse Events(SAE):

Refers to events occurring during a clinical trial that result in death or a serious deterioration in health, including fatal diseases or injuries, permanent defects in

bodily structure or function, hospitalization or prolonged hospitalization, medical or surgical intervention to prevent permanent defects in bodily structure or function, fetal distress, fetal death, or congenital abnormalities, or congenital defects.

Note: The following situations are not considered SAEs:

- Hospitalization that was planned prior to screening and did not result in a serious deterioration in health;
- Expected, non-worsening fluctuations in pre-existing or detected abnormal conditions or diseases at the time of screening;
- Hospitalization or prolonged hospitalization during the clinical trial period as specified in the protocol (if applicable).

4.2.3. Device defects: Not applicable.

4.2.4. Laboratory tests

Collected in the CRF:

- Glucose-related tests:** results of fasting blood glucose, glycated hemoglobin (HbA1c), fasting C-peptide, fasting insulin, and clinical assessment;
- Complete blood count:** results of red blood cells (RBC), white blood cells (WBC), platelets (PLT), hemoglobin (HGB), and clinical assessment;
- Liver and kidney function:** Total bilirubin (Tbil), alanine transaminase (ALT), aspartate transaminase (AST), total protein (TP), albumin, blood urea nitrogen (BUN) or urea (Urea), serum creatinine (Cr), uric acid (UA), estimated glomerular filtration rate (eGFR) test results and clinical assessment;
- Lipid profile:** Total cholesterol (TC), triglycerides (TG), low-density lipoprotein cholesterol (LDL-C), and high-density lipoprotein cholesterol (HDL-C) test results and clinical assessment;

4.2.5. Electrocardiogram (ECG): Not applicable.

4.2.6. Other Assessments:

- Physical examinations:** The CRF collects the following results from participants: height, weight, waist circumference, blood pressure, and pulse rate (during the screening period); weight, waist circumference, blood pressure, and pulse rate (during the follow-up period).
- GA measurement:** The CRF collects the results of GA measurement tests and their clinical assessment (normal, abnormal without clinical significance, abnormal with clinical significance, not tested).
- Pregnancy test:** The CRF collects whether the subject underwent a pregnancy test, the test date, and the result (negative or positive).

4.3. Demographic data and disease characteristics

- Demographic data:** The CRF collects the subject's date of birth, age, gender, and

ethnicity.

- Diabetes diagnosis history:** The CRF collects information on whether the subject is a newly diagnosed type 2 diabetes patient, the date of the first type 2 diabetes diagnosis, whether antidiabetic medications were used in the past three months, the medication name, start date, whether use was continuous, and the end date.
- History of hypoglycemic episodes:** The CRF collects information on whether the subject had a history of hypoglycemic episodes within the year prior to the screening date, the start date, the end date, and whether the episodes were severe.
- Past medical history:** The CRF collects information on whether the subject has a history of relevant medical conditions, the disease name, the start date, whether the condition is ongoing, the end date, and the treatment method.

4.4. Concomitant Medications

The CRF collects information on whether the subject has any concomitant medications during the study period, including the drug name, start date, end date, whether it is ongoing, single dose, dose unit, administration frequency, route of administration, indication, and associated disease name.

4.5. Protocol Deviations and Medication Adherence

Protocol Deviation: Clinical trials must adhere to GCP principles and comply with the trial protocol approved by the Ethics Committee. Any intentional or unintentional deviation from or violation of GCP principles and the trial protocol is referred to as protocol deviation or protocol violation.

Medication Adherence: The CRF collects information on the participant's medication adherence since the last visit, including whether antidiabetic medications were taken as scheduled (never missed, rarely missed [no more than 3 times per week], frequently missed [3 or more times per week], almost never taken, or taken in excess), whether antidiabetic medications were missed or taken in excess since the last visit, the medication name, administration details, and the total missed/overdose total dose, and unit of measurement.

5. Statistical assumptions

Not applicable.

6. Analysis data set

Randomized population: The entire population that received randomization is considered the randomized population.

Full analysis set (FAS): Participants who received randomization, met the study eligibility criteria, and had baseline measurements for the primary efficacy outcome. The FAS analysis follows the intention-to-treat (ITT) principle.

Per-protocol set (PPS): Participants in the FAS who demonstrated good compliance and had no important protocol deviations that affected the primary efficacy assessment (specific criteria will be confirmed during data verification).

Safety set (SS): All participants with at least one safety assessment are included in the safety analysis.

7. Statistical Methods

